There is no provision for influenza vaccination in pregnant women to be given as part of standard antenatal care. Wong and colleagues (14) conducted a randomised controlled trial (RCT) to promote maternal influenza vaccination with one-to-one education as the intervention and showed that the intervention could increase the uptake from 10% to 21.1%. Our team has previously developed an intervention package which was proved effective in increasing influenza vaccine uptake in young children aged from 6 months to 2 years from 13% to 38% (12). The intervention package included: (i) a concise information sheet about the risk of influenza and benefits of influenza vaccination; (ii) semi-completed forms to utilise the Government's subsidy; (iii) contact details of nearby VSS registered clinics that do not charge above the subsidy; and (iv) vaccination reminders. This proposed study will compare influenza vaccine uptake in three groups of pregnant women: (i) a group offered a multi-component intervention package to encourage uptake of influenza vaccine through the VSS; (ii) a group offered the same package and free influenza vaccination as part of routine antenatal care; and (iii), a control group receiving current standard care.

3. Hypotheses and objectives

Hypotheses:

The uptake of seasonal influenza vaccine in pregnant women can be improved by providing mothers with either a multi-component intervention package to encourage influenza vaccine through the VSS or to offer free influenza vaccine as part of routine antenatal care.

Aims:

- 1. To determine whether influenza vaccine uptake in pregnant women can be increased with a multiple component intervention package and with influenza vaccine offered as part of routine antenatal care at no charge
- 2. To improve mothers' knowledge of maternal influenza vaccination
- 3. To explore whether influenza vaccine uptake in children at approximately 1 year old would be increased with the intervention

4. Study design

This is a prospective RCT of two interventions designed to improve influenza vaccine uptake in pregnant women. The study will be conducted in compliance with Declaration of Heisinki, ICH-GCP and standard CONSORT 2010 statement (15).

Subjects

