A previous Hong Kong RCT showed that the influenza vaccine uptake in pregnant women was 4.3% in 2014-2015 (12). Three other local studies showed 3.9% in 2005/06 (10), 6.2% in 2009/10 (13) and 1.7% in 2010/11 (11). Following the COVID-19 pandemic we anticipate that there will be greater awareness and acceptance of influenza vaccines. In a local RCT to promote maternal influenza vaccine uptake conducted by Wong and colleagues in 2013-2015 (14), the uptakes in the control and intervention groups were 10% and 21.1% respectively. They reported that the higher-than-expected vaccination rate in the control group might indicate the study itself increased the knowledge or awareness of influenza vaccination in the control subjects. To ensure we will have enough sample to prove the hypothesis, we assume a baseline uptake of 10% in the sample size calculation. A similar intervention package was effective in increasing influenza vaccine uptake in children aged from 6 months to 2 years by 25 percentage points (12). We expect the improvement in uptake would be more difficult in pregnant women (conservatively around 20 percentage points increase). Because of the different settings and policies in the two study sites, analysis will be stratified by study sites. Based on a required power of 80% and a significance level of 0.05, by using G*Power (version 3.1.9.4), the sample size required in each group is 69, and thus 414 in total in two study sites. Taking into account participants who do not complete the study (about 20% from past experience), the sample size required is 522 in total and 261 in one study site.

6. Study tools

The intervention will include: (i) standard information about the VSS that is available from the CHP through text message in smart phones (same as that for the controls); (ii) key information including highlight of the risks of influenza in pregnant women and infants and the benefits of influenza vaccination to them, a hyperlink to the forms required for the VSS, if necessary, with guidelines to complete, and a hyperlink of DH's website to search for VSS registered clinics that do not charge additional fees for influenza vaccination above the subsidy; (iii) text message reminders for vaccination; (iv) and being

informed that should they prefer they can receive free influenza vaccine during future antenatal followup visit once the vaccine is available.

7. Safety

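### The sample size is right for a 20-point gain tested within each site, but the primary test should combine both sites, and the power at the only uptake gain cited in pregnant women should be stated

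*Protocol*

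**What the plan says.** Section 5 (Selection of subjects) builds the sample size in four steps.

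- **Baseline.** "we assume a baseline uptake of 10% in the sample size calculation". This equals the control-arm uptake of a local trial in pregnant women, in which "the uptakes in the control and intervention groups were 10% and 21.1% respectively". The background section reports the same result and describes that trial's intervention as one-to-one education.
- **Effect.** The gain is taken from a trial in children, where a similar package was effective in "increasing influenza vaccine uptake in children aged from 6 months to 2 years by 25 percentage points (12". The protocol expects pregnant women to be harder to move and lowers the figure to "conservatively around 20 percentage points increase".
- **Error rates.** "Based on a required power of 80% and a significance level of 0.05". Section 8 makes testing two-tailed.
- **Sites.** Because settings and policies differ between the two hospitals, "analysis will be stratified by study sites". The 69 per group is multiplied by three groups and two sites to give 414, then raised to 522 for 20% loss.

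Section 8 (Statistics) names chi-square tests for uptake and counts missing vaccination status as not vaccinated. It does not mention site.

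**The concern.** Two features of the plan combine.

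First, the planning gain is called conservative in the same paragraph that reports a gain of 21.1 − 10 = 11.1 points in the target population. Twenty points is 20/11.1 = 1.8 times that. The protocol uses a baseline equal to that trial's control arm but does not say why it sets the trial's gain aside. The child-trial package also included "ii) semi-completed forms to utilise the Government's subsidy" and contact details of nearby clinics. Here, women get hyperlinks to the forms and to a clinic search page.

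Second, the 80% power attaches to one pairwise comparison within one site. If the primary analysis follows the sizing, each comparison uses only half the women available for it. If it does not, Section 8 gives no rule for bringing the sites together.

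The comparison most exposed is intervention group 1 versus control, because group 1 gets information, forms guidance and reminders but no vaccine at the clinic. If its true gain were near 11 points, separate site tests would more often than not be non-significant, and a useful package could be reported as ineffective.

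**Working it through.** **Inputs.** Baseline 10%, planned gain 20 points, 80% power, 69 per group per site, 20% loss and 10% versus 21.1% come from Section 5. The two-sided 0.05 level and the rule that missing means not vaccinated come from Section 8. Roughly equal allocation to three groups comes from Section 4.

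**Method.** Power is the sum, over all pairs of vaccinated counts (i, j) that the test declares significant at 0.05, of Bin(i; n, p₁) × Bin(j; n, p₂). It is computed for Fisher's exact test and for the uncorrected chi-square test.

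**Step 1: the protocol's own figure.** For 10% versus 30%, Fisher power is 79.97% at n = 68 and 80.7% at n = 69. So 69 is the smallest n per group that reaches 80%, as stated.

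- Completers: 69 × 3 groups × 2 sites = 414.
- Loss: 69/(1 − 0.20) = 86.25, rounded up to 87 per group per site.
- Enrolled: 87 × 3 = 261 per site and 261 × 2 = 522 in total, as stated.

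**Step 2: power at the cited gain in pregnant women.** Combining the sites gives 69 × 2 = 138 completers, or 87 × 2 = 174 randomised, per group. Counting 20% missing as unvaccinated turns 10% into 0.8 × 10% = 8%, and 21.1% into 0.8 × 21.1% = 16.9%.

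| Comparison | n per group | Fisher | Chi-square |
|---|---|---|---|
| One site, completers, 10% vs 21.1% | 69 | 35.8% | 43.9% |
| One site, missing as unvaccinated, 8% vs 16.9% | 87 | 35.4% | 43.0% |
| Both sites, completers, 10% vs 21.1% | 138 | 67.9% | 73.2% |
| Both sites, missing as unvaccinated, 8% vs 16.9% | 174 | 66.7% | 72.3% |
| Both sites, completers, 10% vs 30% | 138 | 98.6% | 99.0% |

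The allowance for loss does not restore the power, because women with missing status count as unvaccinated in both arms.

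**Step 3: gain from combining.** At the cited effect, combining adds 67.9 − 35.8 = 32.1 points (Fisher) or 73.2 − 43.9 = 29.3 points (chi-square), with the same women.

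**Step 4: what the combined test can detect.** With 138 per group and a 10% baseline, Fisher power is 80.2% at 23%, that is, at a gain of 13 points.

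**Step 5: sensitivity to the baseline.** Section 5 also cites 4.3% uptake in pregnant women. With that baseline and the same 11.1-point gain (4.3% vs 15.4%), power is 50% to 62% per site and 85% to 90% combined.

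The combined figures treat the two sites as having the same uptake in each arm. They are simple two-sample calculations that stand in for a site-stratified test.

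**The case against.** The strongest reply is that the sample size contains no error. It delivers 80% power at the stated 20 points, and the word claiming caution can be read as relative to the 25 points seen in children. Choosing one benchmark over another is a planning judgement. That stands, so a reader should not infer that the trial is mis-sized.

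The 11.1-point trial is also not like for like. It tested one-to-one education in 2013-2015, before the subsidy scheme covered pregnant women from 2016/17. The present package has several components. This stands as a reason why a larger gain is possible, but the protocol does not make the argument. The hyperlinks that replace semi-completed forms do not settle it either, since nothing in the protocol shows that they lower uptake.

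A tempting stronger reading is that the trial as a whole has 36% to 44% power. The protocol does not support it, for three reasons.

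- The benchmark bears on group 1 versus control. Group 2 is also offered free vaccine at antenatal visits, and no cited figure points to an 11-point gain there.
- Stratifying by site can equally mean one combined test that respects site. Under that reading, the relevant figures are 68% to 73% on completers, and 79% to 83% if all 174 per arm respond.
- The 10% baseline is higher than the earlier uptakes cited. At 4.3%, the combined test exceeds 80%.

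It would also be too strong to call the 11.1-point trial the only one cited in pregnant women. Another cited trial supplies the 4.3% maternal uptake; the education trial is the only one for which an uptake gain in pregnant women is reported.

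What remains is that Section 5 sizes each site separately, Section 8 is silent on site, and the protocol gives a reason (different settings and policies) for looking at sites individually. That reason justifies reporting results by site. It does not require separate site tests to decide the primary outcome.

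**Conclusion.** The point holds in a limited form. The 69 per group is correct for 10% versus 30% within a site. The description of 20 points as conservative is left unreconciled with the 11.1-point gain in the same paragraph, and the plan does not fix whether the primary result comes from separate site tests or one combined test.

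If group 1 versus control had the cited gain, that choice would move power from about 36% to 44% per site to about 68% to 73% combined. Combining does not reach 80% at 11.1 points on 138 completers per group; it does so at about 13 points.

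These figures assume a 10% control uptake, the same uptake by arm at both sites, two-sided 0.05 for each comparison, and 20% loss as planned. They say nothing about group 2 versus control or group 1 versus group 2. This is an inexpensive improvement to the plan, not the correction of a calculation error.

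**What to change.** **Section 8.** State that the primary test is each intervention arm versus control over both sites combined, stratified by site, using Cochran-Mantel-Haenszel or logistic regression with site as a covariate. Report site-specific estimates and an arm-by-site interaction as secondary, which keeps the protocol's interest in differing settings and policies.

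**Section 5.** Delete the word that calls the 20-point gain conservative. State that 69 completers per group per site give 80% power for a 20-point gain from 10%. Add the combined-site power at 10% versus 21.1% (68% to 73% with 138 completers per group) as a sensitivity figure for group 1 versus control, and note that combined power reaches 80% at a gain of about 13 points.

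**Cost.** Wording in two sections and the same 522 women. The stated power looks less favourable, and site-specific tests become secondary.

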Pregnant women will be recruited antenatally in two public hospitals (Prince of Wales Hospital and Pamela Youde Nethersole Eastern Hospital). A convenience sample of eligible mothers coming for antenatal check-up will be invited to participate in this proposed study. The inclusion criteria to subject selection includes: pregnant women in any trimester; at least 18 years old; Cantonese speaking and able to read Chinese; no serious obstetrical complications; no mental or psychosocial problem that might affect their interpretation of study questionnaires; not yet received influenza vaccine during this pregnancy; have plans to continue most antenatal follow-up at the study hospitals; have plans to remain in Hong Kong after delivery for at least one month; have smart phones; and can provide signed informed consent. Those cannot meet the inclusion criteria will be excluded. There is no withdrawal criterion of this study. Subjects enrolled in the study who later do not wish to be contacted anymore will be regarded as withdrawal.

After enrolment and consenting, all participants will be randomly allocated into either control or intervention groups using block randomisation (16). Three groups will have similar numbers of participants. We will use statistical software R (version 3.5.2) to randomly generate the treatment allocation in random block sizes of 6 to 12 with block size kept unknown to the research assistants carrying out recruitment and interviews. The treatment assignments will be placed in sealed and opaque envelopes with sequential numbers on the covers. Research assistants who will be responsible for study outcomes assessment, will be blinded to treatment allocation, i.e., not generating treatment allocation and not delivering treatments. Also, the principal investigator and partcipants will also be blinded to treatment allocation, i.e., not knowing the grouping of participants.

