Not applicable as this research does not involve any safety issue. Common side effects of influenza vaccination include soreness, redness and swelling where the vaccine was given, mild headache, fever, muscle aches and fatigue.

8. Statistics

Exposures

Intervention Group 1: Type of intervention given: (i) concise information, (ii) provision of and guidance on completing documentation to utilise vaccination subsidy, (iii) a hyperlink of DH's website to search for VSS registered clinics, and (iv) vaccination reminders.

Intervention Group 2: Access to free influenza vaccination at an antenatal clinic follow up visit.

Outcome measures

Primary Outcome measure Influenza vaccine uptake rate in pregnant women

Secondary Outcome measure

Knowledge and attitudes of mothers in relation to influenza disease and influenza vaccine before and after receiving intervention information

Statistical analysis

DMP Tool will be used to prepare a formal data management plan. To ensure data quality, data will be double-entered and validated using EpiData. Intention-to-treat analysis (20) will be used and any missing influenza vaccination status will be taken as no vaccination. Demographic and maternal health factors will be compared between intervention- and control-subjects. Wilcoxon rank-sum tests will be used for continuous variables and chi-square tests for categorical variables. Chi-square tests will be performed to examine the effectiveness of the intervention package in improving influenza vaccination uptake in pregnant women. Each HBM attitude statement will be scored from 1 to 4 (from strongly disagree to strongly agree). Cronbach's alpha (21) will be used to measure internal consistency of HBM constructs. Permutation tests (22) will be used to examine any paired difference in attitude scores before and after intervention delivery. All statistical analyses will be performed using statistical software R (version 3.6.1) and a two-tailed p-value < 0.05 will be taken as statistically significant.

9. Access to data

All personal information will be kept confidential and the use of the data collected will only be restricted in the office of the Department of Paediatrics of The Chinese University of Hong Kong. Access to data is only limited to authorised members of research team under the direction of the principal investigator.

10. Quality control and quality assurance

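### Section 5 sizes each site to stand alone and promises a site-stratified analysis, but Section 8 names only chi-square tests and gives no rule for combining or reconciling the two site results

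*Protocol*

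**What the plan says.** Three parts of the protocol bear on this.

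- **Section 5 (Selection of subjects)** commits to a site-stratified analysis: "Because of the different settings and policies in the two study sites, analysis will be stratified by study sites". The inputs are "we assume a baseline uptake of 10% in the sample size calculation" and an expected gain described as "conservatively around 20 percentage points increase", with 80% power and a 0.05 significance level. The result is that "the sample size required in each group is 69, and thus 414 in total in two study sites". Allowing for about 20% non-completion gives 522, or 261 per site.
- **Section 8 (Statistics, Statistical analysis)** gives the test for the primary outcome: "Chi-square tests will be performed to examine the effectiveness of the intervention package in improving influenza vaccination uptake in pregnant women". The significance rule is that "a two-tailed p-value < 0.05 will be taken as statistically significant". Site does not appear in this section, nor does a combined estimate or a rule for two site results.
- **Section 4 (Study design, Subjects)** says that "all participants will be randomly allocated into either control or intervention groups using block randomisation", with random block sizes of 6 to 12 and numbered envelopes. It does not say whether the list is common to both hospitals or separate for each.

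**The concern.** The total of 414 is the single-site requirement doubled, so the sample size presupposes that each hospital answers the question by itself. The section that fixes the analysis does not carry that through. Three analyses fit the text: separate chi-square tests in each hospital, one chi-square test on the pooled data, or one test stratified by hospital. The first is the most natural reading, and it produces two p-values for each comparison with control. Nothing says whether the trial succeeds when both are significant, when either is, or only when some combination is.

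These rules differ in power and in type I error. If the rule is not fixed beforehand, it can be chosen after the site results are known.

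**Working it through.** **Inputs.** Control uptake 10%, intervention uptake 10% + 20 points = 30%, 80% power, alpha 0.05, 69 per group per site, 20% non-completion (all Section 5); two-sided testing (Section 8); three groups of similar size (Section 4).

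**Reproducing the plan's figure.** Exact power of the two-sided Fisher test, by enumerating two binomials at 10% and 30%, is 79.97% with 68 per group and 80.7% with 69. So 69 is the first size that reaches 80%. (The usual chi-square formula gives 62, or 72 with continuity correction.) Then:

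- 69 × 3 groups × 2 sites = 414
- 69 / 0.8 = 86.25, rounded up to 87 per group per site
- 87 × 3 = 261 per site; 261 × 2 = 522

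The arithmetic is right, and it confirms that each site was sized alone.

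**Site-by-site reading, 69 per arm, same true effect at both sites.** Let p be the exact power at one site: 0.807 (Fisher) or 0.857 (chi-square without correction). The sites are independent.

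| Quantity | Formula | Fisher | Chi-square |
|---|---|---|---|
| One site significant | p | 80.7% | 85.7% |
| Both significant | p² | 65.1% | 73.4% |
| Sites disagree | 2p(1−p) | 31.2% | 24.5% |
| At least one significant | 1−(1−p)² | 96.3% | 98.0% |

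**Type I error if either site suffices.** For tests that run at 5%, the error is 1 − 0.95² = 9.75% per comparison. Simulation of the chi-square test with 10% uptake in every arm gave 9.8% (40,000 replicates). This figure belongs to the chi-square test that Section 8 names. Fisher's test is conservative at this size: enumeration at 10% in both arms gives 2.5% per site, hence 1 − 0.975² = 4.9%.

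**Combined reading, 69 × 2 = 138 per arm.** At 10% versus 30%, simulated power of a Cochran-Mantel-Haenszel test stratified by site is 98.9%. The pooled chi-square gives 98.8% by formula. When true uptake differs by site with no treatment effect (5% at one, 20% at the other, an illustrative assumption), simulated type I error is 4.9% for the stratified test and 4.3% for the pooled chi-square.

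**Sensitivity to the missing-data rule.** Section 8 counts a missing vaccination status as not vaccinated. If 20% are missing in each arm, all 87 per arm per site are analysed and the rates become 0.8 × 10% = 8% and 0.8 × 30% = 24%. Exact power per site is then 79% (Fisher) to 84% (chi-square), 62% to 70% for both sites, and about 98% to 99% combined. The conclusion does not change.

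**The case against.** The strongest reply is that there is no contradiction: Section 5 gives the site rule, Section 8 names the test, and together they mean chi-square tests within each hospital. Differing settings and policies are a legitimate reason to want an answer for each hospital, and the sample was doubled so that each has its 80%. The precise form of a stratified test is also something a statistical analysis plan commonly supplies.

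Much of this stands. A reader might infer any of three stronger claims, and the protocol supports none of them:

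- **That Section 8 prescribes an unstratified test.** It is silent on site, and silence does not override the explicit statement in Section 5.
- **That randomisation is not stratified by site.** Section 4 neither states nor excludes a list per hospital, and a site-stratified analysis is valid either way.
- **That the site-by-site reading leaves the trial underpowered.** Each site keeps its planned power. Power is lower only relative to one combined test, or if both sites must be significant, a rule the protocol does not state.

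It is also fair to say that the stratified and pooled tests hardly differ in power (98.9% against 98.8%), so that contrast is not where the problem lies.

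What the reply does not answer is the step from two site results to one conclusion. The site-by-site reading it defends is the one that creates this gap, and the protocol bases its sample size on that reading without saying how the trial will be judged.

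**Conclusion.** The point holds as a cheap improvement, not as an error that invalidates the plan. The sample size is correctly computed for a single site. What is missing is a rule linking two site-level tests to one conclusion per comparison. Under the plan's own assumptions (10% versus 30%, the same effect at both sites, 69 completers per arm per site), the hospitals give opposite significance results in about 25% to 31% of trials. Depending on the rule adopted, power is anywhere from 65% to 98%. Type I error per comparison rises to about 10% if one significant site is enough and the chi-square test is used. A single site-stratified test avoids the ambiguity, with about 99% power and 5% type I error on the same participants.

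**What to change.** - **Section 8:** for each comparison of an intervention group with control, name one primary test, a Cochran-Mantel-Haenszel test stratified by site, reported with the Mantel-Haenszel risk difference and its 95% confidence interval. Report site-specific results and the site-by-arm interaction as secondary.
- **Section 5:** keep the sample size. State that 80% is the per-site figure and that the combined stratified test has about 99% power at 10% versus 30%.
- **Section 4:** state whether each hospital has its own block list. This is a clarification, not the correction of a demonstrated error.

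The cost is wording, with no extra participants. The downside is that claims about an individual hospital become secondary. If the investigators want site-specific conclusions to remain primary, they should instead state in advance how two differing results will be interpreted and how the 0.05 level is kept. The change should be made before outcome data are seen.

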Influenza vaccination is one of the most effective interventions to prevent influenza infection and associated complications. Inactivated influenza vaccines (IIVs) are recommended for use in people aged 6 months and above, including pregnant women (4). IIVs were 64%-68% effective in preventing influenza-associated hospitalisation in children aged from 6 months to under 6 years during 2015-2016 (5). Influenza vaccine protects both pregnant women (6) and their newborns below 6 months of age (1). Thus pregnant women are in the highest priority group recommended by both World Health Organization (1) and the Scientific Committee on Vaccine Preventable Diseases, the Centre for Health Protection (CHP) (7). Since 2016/17, they have been provided with free or subsidised influenza vaccination by the Hong Kong Government (8). Pregnant women who are Hong Kong residents can receive subsidised influenza vaccine from private practitioners registered in the Vaccination Subsidy Scheme (VSS).

Despite the influenza vaccination recommendations and reports of its safety during pregnancy (9), the uptake of influenza vaccine in pregnant women is still low in Hong Kong. Before the Government's subsidy scheme became available, the influenza vaccine uptake in pregnant women was 1.7%-6.2% (10-13). Previous local studies showed that determinants of influenza vaccination among pregnant women include better knowledge and more positive attitudes in relation to influenza vaccine, being recommended by healthcare professionals, previously vaccinated with influenza vaccine (either mothers themselves or their family members), awareness of vaccination recommendation, having university degree and longer gestation week (10;11;13). It has anticipated that the COVID-19 pandemic may impact on the acceptance of influenza vaccine but data is lacking.

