All participants will be followed up first by text message at three to four weeks after their expected date of delivery by research staff who will be blinded to treatment group allocation. After confirming delivery, an online self-administered questionnaire will be completed by the participants. If the participants cannot complete the questionnaires online, hardcopy of the questionnaires with stamped and addressed return envelopes will be sent to their home. Follow-up by phone will be the last resort. Attachment VII shows the logistic flow of the proposed study. Participants who agree to be followed up at children's age of approximately 1 year will receive text messages around the time for vaccination information.

Data collection

Data will be collected at two to three time-points: at enrolment and at three to four weeks after the expected date of delivery; and optionally at children's approximately 1 year old. All questionnaires will be self-administered (attachment VIII). The following information will be collected at each time point:

- 1. At enrolment
 - Demographic information
 - Age/ year of birth, place of birth, highest educational level attained, occupation, marital status, household members and income, cigarettes and alcohol consumptions, and receiving CSSA or not
 - Personal identifies such as contact numbers, postal and residential address will be recorded in a separate logbook and linked only to the study number
 - Maternal health information
 - Expected date of delivery, gravidity and parity, pregnancy related health problems, and disease history (17)
 - Vaccination information
 - Heard of influenza vaccine, awareness of influenza vaccination recommendations in priority groups (pregnant women, persons aged 50 years or above, and children aged from 6 months and less than 12 years), and awareness and understanding of VSS in priority groups
 - Influenza vaccination history of mothers and family members in the same household
 - Vaccination status during this and previous pregnancies
 - Knowledge and attitudes in relation to influenza disease and influenza vaccine
- 2. At three to four weeks after the expected date of delivery
 - Influenza vaccination information during pregnancy
 - Vaccination status of mothers and family members in the same household
 - Reasons of receiving or not receiving influenza vaccine
 - Recommendations of receiving or not receiving influenza vaccine
 - Maternal health status during pregnancy

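### The primary chi-square test of uptake uses no prognostic covariates, although the protocol names determinants of uptake and collects them at enrolment: avoidable loss of precision, not bias

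*Protocol*

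**What the plan says.** The primary outcome in Section 8 is binary for each woman: "Influenza vaccine uptake rate in pregnant women". The test is fixed in the same section: "Chi-square tests will be performed to examine the effectiveness of the intervention package in improving influenza vaccination uptake in pregnant women". No covariate is named there. Section 5 adds one design factor: "Because of the different settings and policies in the two study sites, analysis will be stratified by study sites". Section 8 does not say how the chi-square test takes up that stratification.

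The background lists determinants of maternal uptake from local studies. They include "better knowledge and more positive attitudes in relation to influenza vaccine, being recommended by healthcare professionals" and also "previously vaccinated with influenza vaccine (either mothers themselves or their family members), awareness of vaccination recommendation, having university degree and longer gestation week". No effect sizes are given.

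The enrolment list in Section 4 (Data collection) covers the usable ones. It has "Influenza vaccination history of mothers and family members in the same household", highest educational level, expected date of delivery (hence gestation), awareness of the recommendations, and knowledge and attitudes. Recommendations to be vaccinated are listed only for later time points.

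On baseline data, Section 8 says: "Demographic and maternal health factors will be compared between intervention- and control-subjects", and "Wilcoxon rank-sum tests will be used for continuous variables and chi-square tests for categorical variables".

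**The concern.** The protocol identifies who is likely to be vaccinated, records it before randomisation, and then leaves it out of the primary comparison. In a randomised trial, adjusting for a baseline factor related to the outcome removes the part of the between-arm difference due to chance imbalance in that factor, and so narrows the interval. Section 4 describes block randomisation and states no stratification factor, so nothing in the described allocation balances these factors either.

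At stake is precision, mainly if the true effect is smaller than planned. The design assumes a 20-point increase, but Section 5 also cites a local maternal trial with 10% versus 21.1%.

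The baseline comparison does not fill the gap. A p-value between randomised arms tests whether chance produced the difference, which is already known. As worded, it covers demographic and maternal health factors, while the enrolment list puts vaccination history under a separate vaccination heading.

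**Working it through.** **1. The plan's own figures.** Inputs from Section 5: 10% versus 30%, 80% power, significance level 0.05 (two-tailed, Section 8), about 20% non-completion.
- Two-sided Fisher exact test: 68 per group gives 79.97% power and 69 gives 80.7%. The stated 69 is reproduced.
- 69 / 0.8 = 86.25, rounded up to 87; 87 × 3 groups × 2 sites = 522. Reproduced.
- The chi-square test planned in Section 8 (pooled variance) needs 62 per group for 80% power and has about 84% at 69. The trial meets its own target without adjustment.

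**2. What one covariate could add.** Let f be the share previously vaccinated, and p1 and p0 the uptake with and without previous vaccination.
- Overall uptake: m = f·p1 + (1 − f)·p0
- Share of outcome variance explained: R² = f(1 − f)(p1 − p0)² / [m(1 − m)]
- Approximate gain in effective sample size: 1/(1 − R²) − 1

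The protocol gives none of f, p1 or p0. All the values below are assumptions.

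| f | p1 vs p0 | Odds ratio | R² | Gain |
|---|---|---|---|---|
| 25% | 29% vs 17% (m = 20%) | 2 | 0.017 | 2% |
| 15% | 40% vs 15% | 3.8 | 0.052 | 6% |
| 25% | 45% vs 12% | 6 | 0.126 | 14% |
| 25% | 60% vs 12% | 11 | 0.237 | 31% |

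Third row in full: m = 0.25 × 0.45 + 0.75 × 0.12 = 0.2025; R² = 0.1875 × 0.33² / (0.2025 × 0.7975) = 0.0204 / 0.1615 = 0.126; gain = 1/0.874 − 1 = 14%.

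A second parametrisation fixes arm-level uptake at 10% and 30% and sets previous vaccination at 10% to 30%. It gives R² of about 0.01–0.02 at an odds ratio of 2, 0.04–0.08 at 4, and 0.10–0.17 at 8. With few women previously vaccinated and a weak association, the gain can therefore be as low as about 1%.

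**3. Effect on power.** The standard error of the risk difference is multiplied by √(1 − R²). Power is by an unpooled Wald test, so its starting value at 69 per arm is 85.8%, not the pooled 84%.

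| Scenario | R² = 0 | 0.05 | 0.10 | 0.20 |
|---|---|---|---|---|
| 10% vs 30%, 69 per arm (one site) | 85.8% | 87.5% | 89.2% | 92.4% |
| 10% vs 21.1%, 69 per arm | 44.5% | 46.3% | 48.4% | 53.0% |
| 10% vs 21.1%, 138 per arm (both sites) | 73.1% | 75.2% | 77.5% | 82.1% |

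**4. Chance imbalance, for scale.** With f = 25% and 69 per arm, the between-arm difference in previous vaccination has standard deviation √(2 × 0.25 × 0.75 / 69) = 7.4 points. Its 95% range is about ±14 points. At 45% versus 12% uptake, that moves the risk difference by 14.4 × 0.33, or about ±4.8 points. The unadjusted standard error already allows for this; adjustment removes most of it.

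**5. Can the data carry the model?** Pooled over sites at 10%/30%/30% uptake, expected events are 138 × 0.70 = 96.6. Two arm terms, site, previous vaccination, gestation and degree make six coefficients, or about 16 events each. At 10%/21.1%/21.1%, events are 138 × 0.522 = 72, or 12 each.

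**The case against.** The strongest case against is that this is a preference about efficiency. A chi-square test of randomised arms is valid, the trial exceeds its stated power, and covariate lists often sit in a statistical analysis plan that is not at hand. All of that is true, and it limits the point to lost precision. It does not remove it: Section 8 fixes the test of uptake itself, so a later plan with an adjusted primary analysis would differ from the protocol.

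A second objection is sparsity. Each site was sized separately, and at 10% uptake one site's control group has about 7 events (69 × 0.10). A multi-covariate model within a site would indeed be thin. Pooled over sites with single-term covariates it is not, provided site-specific results are kept.

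A third is that the spread of gestation is unknown, because Section 4 recruits women according to gestation and expected vaccine availability. That stands, and it is why the illustration uses previous vaccination only.

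A reader might also infer more than the protocol supports:
- That the determinants are strong. The background gives no effect sizes.
- That the analysis ignores all structure. Section 5 stratifies it by site.
- That baseline tests are offered as a substitute for adjustment, or to choose covariates. Section 8 says neither.
- That a rank-sum test is wrong with three arms. It is a proper test for each intervention arm against control.
- That no size of effect will be reported. The outcome is an uptake rate, and Section 8 does not restrict reporting to p-values.

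**Conclusion.** The point holds as lost precision. Section 8 leaves out of the primary test baseline factors that the protocol itself names as determinants and collects before randomisation. There is no bias, the test is valid, and the trial is not short of its stated power at 10% versus 30%; reading this as an invalid or underpowered primary analysis would go beyond the documents.

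The size cannot be derived from the protocol. Under the assumed inputs, one covariate is worth about 2% (odds ratio near 2) to 31% (odds ratio near 11) more participants. For R² of 0.05 to 0.20 the gain is about 2 to 7 power points at the design effect with 69 per arm, and about 2 to 9 points at 10% versus 21.1%. The baseline p-values do no harm to the primary inference but carry no information.

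**What to change.** Amend Section 8, and the statistical analysis plan if there is one, before outcome data are seen:

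- **Primary estimate.** For each intervention-versus-control comparison, report a standardised (g-computation) risk difference with 95% confidence interval. Take it from a pre-specified logistic model, pooled over sites, with arm, site, previous influenza vaccination (yes/no), gestation at enrolment (from expected date of delivery) and university degree (yes/no).
- **Missing covariates.** State one simple rule, so that no randomised woman is dropped for a missing baseline item.
- **Supportive analyses.** Keep the site-stratified chi-square test, stated explicitly (for example as Cochran-Mantel-Haenszel), and the site-specific results for which the sample was sized.
- **Baseline table.** Describe baseline factors, including vaccination history, by the three arms without p-values.

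The cost is a change of wording and some programming. All the variables are already on the enrolment questionnaire, and the sample size does not change.
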